5.3.1.2 Dosage modification for drug related toxicity

AES grade III or IV that have not reduced to grade II or less at the time that the next dose is due and are considered related to the study drug will be subject to dose modification or hold.

Toxicity	Parameters	Dose adjustment
Neutropenia	ANC < 1000	Withhold dose until > 1000 and reduce next scheduled dose from 20 mg/m2 to 15 mg/m² If reduced dose tolerated, dose may be escalated back to 20 mg/m2 at the discretion of the investigators.
Thrombooutononia	< 50,000	Reduce next scheduled dose from 20 mg/m2 to 15 mg/m² If reduced dose tolerated, dose may be escalated back to 20 mg/m2 at the discretion of the investigators.
Thrombocytopenia	< 25,000	Withhold dose until > 25,000 and reduce next scheduled dose to 15 mg/m² If reduced dose tolerated, dose may be escalated back to 20 mg/m² at the discretion of the investigators.
Peripheral neuropathy	Affecting ADLs	Hold until resolved to baseline and reduce next scheduled dose to 15 mg/m ² If reduced dose tolerated, dose may be escalated back to 20 mg/m ² at the discretion of the investigators.
Nephrotoxicity	SCr > 2 x baseline or eGFR reduced by 50%	Hold until resolved to baseline and reduce next scheduled dose to 15 mg/m ² If reduced dose tolerated, dose may be escalated back to 20 mg/m ² at the discretion of the investigators.

	Mild to moderate liver dysfunction: defined as 2 consecutive values, at least 28 days apart, of: (1) Total Bili (>33% direct) . 1x ULN to < 3xULN	25% dose reduction. Dose may be re-escalated if liver function tests return to normal (baseline) and drug-induced hepatotoxicity is excluded.	
Hepatotoxicity	OR (2) An elevation of AST and/or ALT with normal bilirubin Grade 3 elevation in ALT and/or AST (>5xULN)	Hold until resolved to baseline. Monitor any abnormality weekly. Resume carfilzomib with a 25% dose reduction (15 mg/m²) if drug-induced hepatotoxicity is excluded. If reduced dose tolerated, dose may be escalated back to 20 mg/m² at the discretion of the investigators.	
	Grade 3 elevation in total bilirubin	Hold Carfilzomib until resolution to baseline. Monitor total bilirubin and direct bilirubin weekly. Upon resolution of total bilirubin to normal, resume carfilzomib dosing with a 25% dose reduction if drug-induced hepatotoxicity is excluded.	
	Drug-Induced hepatotoxicity (attributable to carfilzomib	Discontinue carfilzomib.	
		If PRES is suspected, hold carfilzomib. Consider	
Posterior Reversible Encephalopathy Syndrome (PRES)		evaluation with neuroradiological imaging, specifically MRI, for onset of visual or neurological symptoms suggestive of PRES. If PRES is confirmed, permanently discontinue carfilzomib. If the diagnosis of PRES is excluded, carfilzomib administration may resume at same dose, if clinically appropriate.	
Encephalopathy Syndrome		specifically MRI, for onset of visual or neurological symptoms suggestive of PRES. If PRES is confirmed, permanently discontinue carfilzomib. If the diagnosis of PRES is excluded, carfilzomib administration may resume at same dose, if	

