4.4.3 Safety outcomes

Safety outcomes of the study include the following:

- 4.4.3.1 Non-lung irreversible end-organ failure (e.g., end-stage renal disease) any time after day 1 attributable to carfilzomib.
- 4.4.3.2 Incidence of adverse effects (AE) requiring dose-modification (see section 5.3.1.2) any time during days 1-16.
- 4.4.3.3 Incidence of any AE at any time after day 1 as graded by the NIH Common Terminology Criteria for Adverse Events (CTCAE) (appendix B) criteria, as follows:
 - Grade 1: Mild; asymptomatic or mild symptoms; clinical or diagnostic observations only; intervention not indicated.
 - Grade 2: Moderate; minimal, local or noninvasive intervention indicated; limiting ageappropriate instrumental ADL (Instrumental ADL refer to preparing meals, shopping for groceries or clothes, using the telephone, managing money, etc.).
 - Grade 3: Severe or medically significant but not immediately life-threatening; hospitalization or prolongation of hospitalization indicated; disabling; limiting self-care ADL (self-care ADL refer to bathing, dressing and undressing, feeding self, using the toilet, taking medications, and not bedridden).
 - Grade 4: Life-threatening consequences; urgent intervention indicated.

Grade 5: Death related to AE.

- 4.4.3.4 Incidence of hypogammaglobulinemia any time after day 1.
- 4.4.3.5 Incidence of culture-proven *de novo* infection any time after day 1.
- 4.4.3.6 Diagnosis of systemic inflammatory response syndrome (SIRS) any time during days 1-16; requiring at least 2 of the following 4 criteria:

Body temperature: < 36 or > 38 degrees Celsius

Tachycardia: > 90 beats per minute

Tachypnea: > 20 breaths per minute

White blood cells: < 4000 or > 12000 cells/mm³

- 4.4.3.7 Patient death at any time after day 1 attributable to carfilzomib.
- A 1:1 retrospective control group including lung transplant recipients from the University of Pittsburgh with Antibody Mediated Rejection will be created to describe differences in the endpoints using the CFZ-based regimen vs. historic standard of care.

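### The lead sentence of 5.3.1.2 and its table set different conditions for modifying a dose, no text says which governs, and safety outcome 4.4.3.2 inherits the ambiguity

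*Combined protocol and SAP*

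**What the plan says.** All of this is in the combined protocol and SAP.

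- **Lead sentence of 5.3.1.2.** It names "AES grade III or IV that have not reduced to grade II or less at the time that the next dose is due" and adds that those which "are considered related to the study drug will be subject to dose modification or hold". It therefore sets three joint conditions: grade, lack of recovery, and relatedness.
- **Neuropathy and nephrotoxicity rows.** "Hold until resolved to baseline and reduce next scheduled dose to 15 mg/m" (that is, 15 mg/m²). The neuropathy trigger is any effect on activities of daily living (ADL), with no grade given.
- **Liver rows.** One begins "Mild to moderate liver dysfunction: defined as 2 consecutive values", requires the two values to be at least 28 days apart, and reduces the dose by 25%. The grade 3 ALT/AST row holds to baseline, then says "Resume carfilzomib with a 25% dose reduction", on condition that a drug cause has been excluded. The grade 3 bilirubin row works the same way. Liver injury attributed to carfilzomib leads to discontinuation.
- **PRES row.** The drug is held on suspicion.
- **4.4.3.2.** The outcome is "Incidence of adverse effects (AE) requiring dose-modification (see section 5.3.1.2) any time during days 1-16".
- **4.4.3.3.** "Grade 2: Moderate; minimal, local or noninvasive intervention indicated"; this grade includes limited instrumental ADL. Limited self-care ADL is placed in Grade 3.

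**The concern.** An investigator who applies the lead sentence and one who applies the table can both claim to follow 5.3.1.2, yet give different doses to patients with the same course.

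The statistical consequence comes through 4.4.3.2. That outcome counts events requiring modification under this section, so its numerator depends on which text is taken to define the requirement. The summaries of total dose and flagged modifications in 5.13.1 would also mix two rules. The use is off label (4.1) and establishing safety is among the stated aims (3.1), so an ambiguous count of dose-modifying toxicity matters even in a descriptive pilot.

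**Working it through.** **The plan's own figure.** A 25% reduction from 20 mg/m² is 20 × (1 − 0.25) = 15 mg/m². This reproduces, so the reduced dose level is not in dispute. The conflict is over when it applies.

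**The two texts side by side**

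| Condition | Lead sentence | Table |
|---|---|---|
| Recovery | No longer met once the event is grade II or less when the next dose is due | Neuropathy, nephrotoxicity, grade 3 ALT/AST and grade 3 bilirubin rows hold to baseline |
| Severity | Grade III or IV | The ADL trigger for neuropathy reaches Grade 2 (instrumental ADL, 4.4.3.3); the mild-to-moderate liver row acts below grade III |
| Causality | Related events | Grade 3 liver rows: reduced dose if a drug cause is excluded, discontinuation (an action the lead sentence does not list) if attributable; PRES held on suspicion |

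**Worked case.** The inputs are 20 mg/m² on days 1, 2, 8, 9, 15 and 16 (section 4 and 5.3.1.1), so the gaps between doses are 1, 6, 1, 6 and 1 days. Suppose a related neuropathy is grade 3 after day 2, grade 2 by day 8 and at baseline by day 15. Assume that it affects ADL until it resolves and that held doses are omitted rather than made up.

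- Lead sentence: the event is grade 2 when the day 8 dose is due, so the sentence is not met. Cycle total 6 × 20 = 120 mg/m²; not counted in 4.4.3.2.
- Table: days 8 and 9 are held, and days 15 and 16 are given at 15. Cycle total 2 × 20 + 2 × 15 = 70 mg/m²; counted.
- Variants under the table: re-escalated on day 16, 2 × 20 + 15 + 20 = 75 mg/m²; baseline never reached, 2 × 20 = 40 mg/m².

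**Effect on 4.4.3.2.** With N = 30, one patient is 1/30 = 3.3 percentage points. Exact (Clopper-Pearson) 95% intervals:

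| Patients counted | Incidence | 95% CI |
|---|---|---|
| 0/30 | 0% | 0 to 11.6% |
| 1/30 | 3.3% | 0.1 to 17.2% |
| 3/30 | 10.0% | 2.1 to 26.5% |

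**Reach of the mild-to-moderate liver row.** If the first value is on day 1, the second cannot fall before day 1 + 28 = day 29, after the last cycle-1 dose. To act by day 16, the first value must date from day 16 − 28 = day −12 or earlier. The row conflicts with the lead sentence in wording, but it can hardly alter the days 1-16 count in cycle 1.

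**The case against.** The strongest reply is that the lead sentence never says it covers these events exclusively. Read as a default, with the table giving specific rules for named toxicities, most of the conflict reduces to a missing sentence on precedence. That reading is reasonable and may be what was intended. However, the protocol does not state it, and the opposite reading, in which the sentence gates the table, is equally open. The two give different doses and counts.

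Four further points limit the concern, and they stand.

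- The liver rows can be read as a sequence: hold, assess cause, then discontinue or resume. The initial hold is compatible with the lead sentence. What remains is a reduced dose after a drug cause is excluded, and an action the sentence does not name.
- Neuropathy limiting self-care ADL is Grade 3 and meets the lead sentence's severity condition. Only the instrumental-ADL case is in doubt on severity.
- Rows that are silent on relatedness sit under a heading about drug-related toxicity, so their silence is not a contradiction.
- Appendix B records any other carfilzomib dose and the reason on each dosing day, so the dose actually given can be recovered.

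A reader might also infer that a neutrophil nadir which recovers between doses shows the same conflict. The documents do not support that. The row says "Withhold dose until > 1000 and reduce next scheduled dose from 20 mg/m2", and withholding can be read to presuppose a dose falling due while the count is low. Nor do the documents give laboratory cut-offs for grades, so the neutrophil, platelet and creatinine triggers cannot be matched to grade III.

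**Conclusion.** The conflict is real. For at least one plausible course, the two texts in 5.3.1.2 give 120 versus 70 mg/m² over a cycle and opposite classifications in 4.4.3.2. Each such patient moves the incidence by 3.3 points. This is more than missing detail, because both rules are written down and they disagree.

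The worked totals rest on the assumed course and on held doses being omitted.

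Two larger claims are tempting and should not be made.

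- **Number affected.** A reader might apply the Grade 3+ rates in 6.1.4 and get 30 × 0.157 = 4.7 patients with neutropenia and 30 × 0.232 = 7.0 with thrombocytopenia. Those are all such events at rates from earlier carfilzomib trials, not the subset for which the two texts differ. That subset cannot be estimated from the documents.
- **Uninterpretable dose data.** Delivered dose and reason are recorded, and this is a single-centre trial, so there is no between-site divergence. What is unclear is which events required modification, and that is what 4.4.3.2 counts.

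**What to change.** 1. The sponsor's clinicians should reconcile the lead sentence of 5.3.1.2 with the table and state which governs for the toxicities the table names. For each row, the text should say how recovery before the next dose, grade and relatedness apply. No dose or clinical rule is proposed here.
2. 4.4.3.2, and its counterpart in the synopsis, should then state whether reductions, holds, omissions and discontinuations under the governing text each count. At present the lead sentence distinguishes modification from hold, while the outcome mentions only modification.

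The cost is a wording amendment to one section and one outcome definition, with the IRB communication that 7.4 already requires. No new data or patients are needed.

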5.3.2 Concomitant therapy

Conventional therapy for AMR: Therapeutic plasma exchange (PLEX) 1.5 plasma volumes replaced with 5% albumin or fresh frozen plasma for 8 sessions every-other day. Total intravenous immunoglobulins (IVIG) 100 mg/kg IV after each PLEX with the exception of the final PLEX where IVIG 500 mg/kg will be given. On day 16, if the IgG level is below 700 mg/dL, an additional dose of IVIG 500 mg/kg will be administered. If the IgG result is found to be 700ml/dL or higher, the IVIG 500mg/kg dose will not be administered. Premedications will be given for IVIG as follows: acetaminophen 650 mg PO and diphenhydramine 25 mg PO both 30 minutes prior to IVIG, unless otherwise directed on the part of one of the investigators if believed to be in the best interests of patient care. Conventional therapy requires an inpatient hospital stay. Patients will receive a tunneled PLEX catheter and peripherally inserted central catheter (PICC) inserted by interventional radiology in the routine clinical care of these patients prior to receiving any conventional or carfilzomib therapy.

Contraception

Female:

Women of childbearing potential must either agree to abstain from sexual intercourse or use an effective birth control method during treatment with carfilzomib. Given that carfilzomib was clastogenic in the in vitro chromosomal aberration test in peripheral blood lymphocytes, as a precaution, females of childbearing potential and/or their male partners should use effective contraception methods or abstain from sexual activity during and for 30 days after treatment with carfilzomib. If pregnancy occurs during this time, patients should be apprised of the potential hazard to the fetus. Kyprolis (carfilzomib) should only be used during pregnancy if the potential benefits to the mother outweigh the potential risks to the fetus.

Based on its mechanism of action and findings in animals, carfilzomib can cause fetal harm when administered to a pregnant woman. Carfilzomib caused embryo-fetal toxicity in pregnant rabbits at doses that were lower than in subjects receiving the recommended dose. Carfilzomib administered to pregnant rats and rabbits during the period of organogenesis was not teratogenic at doses up to 2 mg/kg/day in rats or up to 0.8 mg/kg/day in rabbits. If carfilzomib is used during pregnancy, or if the subject becomes pregnant while taking this drug, she should inform the investigator or study staff immediately. The investigator should notify Amgen of the pregnancy and discuss follow-up with the subject. It is not known if carfilzomib will reduce the efficacy of oral contraceptives. Due to an increased risk of venous thrombosis associated with carfilzomib, subjects currently using oral contraceptives or a hormonal method of contraception associated with a risk of thrombosis should consider an alternative method of effective contraception.

Male:

Males of reproductive potential should be advised to avoid fathering a child while being treated with carfilzomib. The potential for carfilzomib to be transferred via semen and its effect on sperm are unknown. Male subjects treated with carfilzomib and/or their female partners (if of childbearing potential) should use effective contraceptive methods or abstain from sexual activity while treated with carfilzomib and refrain from donating sperm while on carfilzomib and for 90 days after treatment. If pregnancy occurs during this time, patients should be apprised of the potential hazard to the fetus, study drug should be interrupted, and a serum pregnancy test

performed. Study drug administration may resume if result is negative and study drug be discontinued, if positive.

Male subjects should be advised to inform the investigator or study staff immediately in the event that their female partner becomes pregnant during the study. Upon receipt of this information, the investigator should notify Amgen of the pregnancy and discuss follow-up regarding the pregnancy outcome with the subject.

Breastfeeding:

If a woman breastfeeds during the study, she must inform the investigator or study staff immediately. The investigator should notify Amgen that the subject has breastfed the infant and discuss follow-up with the subject.

It is not known whether Kyprolis is present in human breast milk. Due to the potential for adverse effects in nursing infants from carfilzomib, a decision should be made whether to discontinue nursing or to discontinue Kyprolis, taking into account the potential benefit of carfilzomib to the mother.

No studies of carfilzomib have been conducted in breastfeeding women. Carfilzomib should not be used during breastfeeding. Breastfeeding women and women planning on breastfeeding may not participate in clinical trials with carfilzomib.

A Woman of Childbearing Potential (WOCBP)

Any female who has experienced menarche and is not postmenopausal (i.e., has had menses at any time in the preceding 12 consecutive months).

Highly effective method of contraception / birth control include:

Combined (estrogen and progestogen) hormonal methods: pills, vaginal ring, or skin patch
Single hormonal methods (progestogen) to stop release of the egg from the ovary:
[pills, shots/injections, implants (placed under the skin by a healthcare provider)]
Intrauterine device (IUD)
Intrauterine hormonal-releasing system (IUS)
Surgery to tie both fallopian tubes (bilateral tubal ligation/occlusion)
Your male partner has had a vasectomy and testing shows there is no sperm in the semen
Sexual abstinence (not having sex)

Barrier Contraceptive as defined in ICH (M3)

A contraceptive device that physically prevents sperm from entering the endometrial cavity and fallopian tubes (e.g. male condom, female condom or diaphragm).

5.3.3 Excluded therapy

The following medications must be discontinued prior to enrollment: Eculizumab (Soliris)
Rituximab (Rituxan)
Cyclophosphamide IV (Cytoxan)

5.4 Study assessments

See appendix B for full listing of study data collection.

Study therapy will be given as an inpatient. Screening patients for AMR as defined above in section 4.3 for enrollment in the trial may occur as an inpatient or outpatient. Patients will undergo a minimum 16 day hospitalization for conventional AMR therapy and for study carfilzomib. Patients may return to the clinic for standard of care visits on days 28 and 42 and 90 (2 and 4 and 10 weeks post therapy completion) for assessment as described below.

Patients will be followed in the study until day 90. There are no follow-up visits as part of this research study, however, if patients return to their standard of care routine visits, a medical record review will be performed to obtain this data from patients' medical records, whenever available. Patients will be subsequently followed by their treating physician under routine clinical care for recurrent AMR until they expire and any available clinical information related to their standard lung transplant care will be obtained from medical records up to 360 days.

For patients who prematurely discontinue therapy, all future planned study and routine clinical care assessments will be completed unless the patient expires. An assessment for the purpose for premature discontinuation will be taken at the time of study discontinuation.

The University of Pittsburgh laboratories will be used to assess all samples. DSA samples will be processed by the University of Pittsburgh Histocompatibility Lab under the direction of co-investigator [name]. PBMC isolation, and exploratory testing samples will be process by the research lab of co-principal investigator [name].

5.4.1 Definition of study assessments

Standard of Care procedures:

History and Physical Exam: A complete patient history and physical exam includes the evaluation of the head, ears, eyes, nose, and throat (HEENT), cardiovascular, dermatological, musculoskeletal, respiratory, gastrointestinal, and neurologic systems. Changes from baseline abnormalities will be recorded at each subsequent physical examination. New or worsened abnormalities will be recorded as AEs if deemed to be related to study therapy.

Complete blood count: white blood cell count, hemoglobin, hematocrit, and platelet count. WBC differential: absolute neutrophil, lymphocyte, eosinophil, and monocyte counts.

Complete metabolic panel (CMP): sodium, potassium, chloride, bicarbonate, blood urea nitrogen, serum creatinine, glucose, calcium, magnesium, phosphorus, AST, ALT, Alkaline phosphatase, and total bilirubin levels.

Pulmonary function tests: forced expiratory volume in 1 second, forced vital capacity, forced expiratory flow.

Biopsy: transbronchial forceps biopsy.

Luminex SAB: whole blood draw for processing by the HLA lab.

Luminex C1g-SAB: whole blood draw for processing by the HLA lab.

Complement 3 and 4: whole blood draw for processing by the UPMC basic laboratory.

Research Procedures:

Pregnancy test: all women of childbearing potential will have a serum pregnancy test within 7 days prior to study drug administration.

Total IgG and IgG subclasses: whole blood draw for processing by the HLA lab. This samples will only be obtained if patient is coming to their standard of care visit on days 28, 42 and 90 (±14 days).

Blood for PBMC: whole blood draw for processing by the [name] lab. This sample will only be obtained if patient is coming to their standard of care visit on days 28, 42 and 90 (±14 days).

5.5 Screening and pretreatment assessments

All screening evaluations must be completed and reviewed to confirm that patients meet all eligibility criteria before the first infusion of carfilzomib. Written informed consent for participation in the study must be obtained before performing any study-specific screening tests or evaluations. Informed consent forms will be maintained at the study site. Refer to Section 4, table 4 for specific delineations.

5.6 Assessments during treatment

All visits must occur within ± 14 days of the scheduled data, unless otherwise noted. Assessments scheduled on the day of study drug administration should be performed prior to study drug infusion, unless otherwise noted. We will collect results from medical records from procedures done as Standard of Care (biopsies, PFTs, bronchoscopies, physical exam, lab results, PLEX and IVIG). Standard of Care procedures will not be done solely for research purposes.

5.7 Study completion

Patients discontinued from the study early (dropout) will be asked to return to the clinic within 30 days after the last infusion of carfilzomib for a follow-up visit.

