Carfilzomib dosing schedule: Carfilzomib will be administered on the multiple myeloma schedule consisting of 20 mg/m² on days 1, 2, 8, 9, 15, and 16 to constitute one therapeutic cycle. On PLEX/IVIG days, carfilzomib will be given in between PLEX and IVIG to avoid inadvertent blockade of the Fcγ receptor. Carfilzomib will be delivered via central access IV over 30 minutes (+15 minutes); slowed to 60 minutes (+15 minutes) if infusion reactions occur. Carfilzomib will be diluted in a total of 80 mL dextrose 5% water (D5W) for administration. Premedications for carfilzomib administration will be given as follows: acetaminophen 650 mg PO, diphenhydramine 25 mg PO, ondansetron 4 mg PO, prednisone 40 mg PO or methylprednisolone 40 mg IV, all at least 30 minutes prior to and not more than 6 hours before carfilzomib, unless otherwise directed on the part of one of the investigators if believed to be in the best interests of patient care. Preinfusion hydration with a one-time bolus of 250 mL 0.9% sodium chloride will be given at least 30 minutes prior to and not more than 6 hours before carfilzomib to minimize the nephrotoxic AE. Postinfusion hydration with a one-time bolus of 250 mL 0.9% sodium chloride may be given immediately after carfilzomib to minimize the nephrotoxic AE

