4.3.9 Hypogammaglobulinemia, total serum IgG < 700 mg/dL

4.4 Study Endpoints

4.4.1 Primary endpoint

The primary endpoint of this study is the absolute change in DSA strength, titer, and complement fixation from day 1 to day 42. DSA strength will be determined by Luminex single-antigen bead testing in the neat serum and quantitated in units of mean fluorescent intensity. DSA titer will be determined by Luminex single-antigen bead testing in the diluted serum to 1:16 and quantitated in units of mean fluorescent intensity. DSA complement fixation will be determined by C1q-based Luminex single-antigen bead testing in the neat serum and quantitated in units of mean fluorescent intensity.

A 1:1 retrospective control group including lung transplant recipients from the University of Pittsburgh with Antibody Mediated Rejection will be created to describe differences in the endpoints using the CFZ-based regimen vs. historic standard of care.

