5.3.1.1 Dosage, administration, and storage

Carfilzomib dosing schedule: Carfilzomib will be administered on the multiple myeloma schedule consisting of 20 mg/m² on days 1 2, 8, 9, 15, and 16 (one cycle) to constitute one therapeutic cycle. On PLEX/IVIG days, carfilzomib will be given in between PLEX and IVIG to avoid inadvertent blockade of the Fcγ receptor. Carfilzomib will be delivered via central access IV over 30 minutes (+15 minutes); slowed to 60 minutes (+15 minutes) if infusion reactions occur.

Carfilzomib will be diluted in a total of 80 mL dextrose 5% water (D5W) for administration. Premedications for carfilzomib administration will be given as follows: acetaminophen 650 mg PO, diphenhydramine 25 mg PO, ondansetron 4 mg PO, prednisone 40 mg PO or methylprednisolone 40 mg IV, all at least 30 minutes prior to and not more than 6 hours before carfilzomib, unless otherwise directed on the part of one of the investigators if believed to be in the best interests of patient care. Preinfusion hydration with a one-time bolus of 250 mL 0.9% sodium chloride will be given at least 30 minutes prior to and not more than 6 hours before carfilzomib to minimize the nephrotoxic AE. Postinfusion hydration with a one-time bolus of 250 mL 0.9% sodium chloride may be given immediately after carfilzomib to minimize the nephrotoxic AE

Carfilzomib may be administered for 1-2 complete cycles in the study. A second cycle may be given for lack of resolution of AMR or for continued detection of DSA in the absence of allograft improvement. If > one cycle is needed, the patient must still meet the enrollment criteria prior to the second cycle, and must not have had improvement after the first cycle or have experienced regression from initial improvement to qualify for a second study cycle. If > two cycles are desired, these must be given outside of the study. If > two cycles are desired, the third cycle must not be given within 90 days of day 1 of the first cycle. If the third cycle begins within this 90 day period, this will constitute a protocol violation.

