5.9 Patient discontinuation

Patients will be removed from study continuation if the toxicities of therapy are deemed by the investigators to outweigh the potential benefit of therapy. Such toxicities may include severe thrombocytopenia (platelets < $10,000 \times 10^6$), acute kidney injury requiring renal replacement therapy, or severe hepatitis (ALT > 1000), or others deemed relevant to the individual patient by the investigators.

If patients discontinue study drug early, these patients may be replaced in the study by patients who are likely to complete at least 1 cycle of carfilzomib.

The investigators have the right to discontinue a patient from the study for any medical condition that the investigator determines may jeopardize the patient's safety if he or she continues in the study or if the investigator determines discontinuation is in the best interest of the patient.

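### Sections 5.4, 5.7 and 5.9 conflict on follow-up after carfilzomib is stopped for toxicity, leaving it unclear whether day-42 and day-90 DSA and FEV1 must still be retrieved

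*Combined protocol and SAP*

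**What the plan says.** Three sections of the combined protocol and SAP bear on a patient who stops carfilzomib because of toxicity.

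- **Section 5.4 (Study assessments):** "For patients who prematurely discontinue therapy, all future planned study and routine clinical care assessments will be completed unless the patient expires". Its next sentence records the reason for stopping at the time of study discontinuation, so the section itself mixes stopping drug with leaving the study.
- **Section 5.9 (Patient discontinuation)** sets the removal rule: "Patients will be removed from study continuation if the toxicities of therapy are deemed by the investigators to outweigh the potential benefit of therapy". It also allows replacement: "If patients discontinue study drug early, these patients may be replaced in the study by patients who are likely to complete at least 1 cycle".
- **Section 5.7 (Study completion)** sets the dropout rule: "Patients discontinued from the study early (dropout) will be asked to return to the clinic within 30 days after the last infusion of carfilzomib". No assessments are named for that visit.

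The timing that matters is set elsewhere. Section 4.4.1: "The primary endpoint of this study is the absolute change in DSA strength, titer, and complement fixation from day 1 to day 42". Section 4.4.2 adds DSA change to day 90 and FEV1 change to days 42 and 90. Section 5.6: "All visits must occur within ± 14 days of the scheduled data, unless otherwise noted".

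**The concern.** Sections 5.4 and 5.7 could be read as covering different people: those who stop drug, and those who leave the study. Section 5.9 closes off that reading for toxicity, because it takes a patient whose treatment has become too toxic and removes that patient from the study. The same person then falls under 5.4 (all later assessments) and under 5.7 (a return visit within 30 days of the last infusion). No section ranks the rules.

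Patients stopped for toxicity received the least drug and tolerated it worst. If staff take 5.7 and 5.9 as the operative rules, they may not look for these patients' day-42 and day-90 DSA and FEV1 values. The missingness would then be tied to toxicity and low exposure, and the change-from-baseline summaries would lean toward patients who tolerated treatment. Section 5.13 defines no analysis population and no handling of missing values that would offset this.

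**Working it through.** **Inputs**

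- Infusion days in cycle 1 (Section 4): "20 mg/m² on days 1, 2, 8, 9, 15, and 16 to constitute one therapeutic cycle". An early stop therefore has its last infusion on day 1, 2, 8, 9 or 15; day 16 completes the cycle. Infusions are assumed to fall on their nominal days.
- Exit visit (5.7): at most 30 days after the last infusion.
- Visit window (5.6): ±14 days.
- Second cycle (5.3.1.1): "Carfilzomib may be administered for 1-2 complete cycles in the study". Its start day is not fixed.
- Enrollment (5.13.3): 10 per year × 3 years = 30, which matches the stated 30. It rests on accrual, and no stopping or dropout rate is given.

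**Windows**

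- Day 28: 28 ± 14 = days 14–42.
- Day 42: 42 ± 14 = days 28–56.
- Day 90: 90 ± 14 = days 76–104.

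**Latest 5.7 visit = last infusion day + 30**

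| Last infusion | Latest visit | Reaches day 42? | Inside 28–56? | Short of day 76 | Short of day 90 |
|---|---|---|---|---|---|
| 1 | 31 | no | yes | 45 | 59 |
| 2 | 32 | no | yes | 44 | 58 |
| 8 | 38 | no | yes | 38 | 52 |
| 9 | 39 | no | yes | 37 | 51 |
| 15 | 45 | yes | yes | 31 | 45 |

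These are latest days; an earlier visit, even before day 28, also satisfies 5.7. For a last infusion on day 16 the latest visit is day 46, 30 days short of day 76.

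**Second cycle.** To reach the day-90 window the last infusion must be on day 76 − 30 = 46 or later; to reach day 90 itself, on day 90 − 30 = 60 or later. Only a patient stopped in a second cycle could meet either.

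**Overlap.** The day-28 and day-42 windows share days 28–42. A sample on day 31 qualifies for both, and no rule assigns it.

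**Number affected (assumed rates).** 10% of 30 = 3 patients, leaving 27 with full follow-up; 20% = 6, leaving 24. If SD is unchanged, the standard error of a mean change rises by √(30/27) = 1.05 to √(30/24) = 1.12. That loss of precision is modest; the larger worry is that the missing patients are selected by toxicity.

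**The case against.** The strongest reply is that the sections can be read together. Section 5.7 asks for a visit; it does not say that this is the only visit or that collection then ends. Section 5.4 is explicit, and on this reading a site that stopped collecting would breach it. That reading is available, but 5.9's removal from the study pulls against it and nothing in the text settles the matter. So a reader should not infer that omitting later data is plainly compliant. It is compliant only if 5.7 and 5.9 override 5.4.

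Four further objections limit the point, and each stands.

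- **Adverse events.** A reader might infer that safety data end with the exit visit. They do not. Section 6.2.1 requires recording on days 28, 42 and 90 (±14), 6.2.2 provides telephone contact, 5.8 follows ongoing related events, and 6.5 follows all serious events to resolution or stabilization. None exempts removed patients. What is unclear is only whether new non-serious events are still solicited after removal.
- **Routine care.** A reader might infer that these patients would certainly have no day-90 outcome. The DSA assays and lung function tests are standard-of-care procedures taken from records. Section 5.4 obtains available clinical data up to 360 days, and Appendix A continues record review for all patients alive at day 90. A patient who stops drug but attends routine visits can have values. Conversely, there are no research follow-up visits and no standard-of-care test is done solely for research, so completers can lack values too.
- **Day 42.** Every latest exit day lies inside the ±14-day window, so the protocol's own standard can be met. The question of which sample counts as day 42 arises for all patients.
- **Stopping rate.** The 10–20% is assumed; no figure in the documents supports it.

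**Conclusion.** The conflict is real and should be resolved before data are summarized. Sections 5.4, 5.7 and 5.9 give incompatible answers on whether the study must go on collecting data from a patient removed for toxicity. If 5.7 and 5.9 are followed, the one visit they ask for need not reach nominal day 42 and, for any cycle-1 stop, cannot reach the day-90 window. The consequence is a risk, not a certainty, that day-42 and day-90 DSA and FEV1 go unretrieved in the patients who tolerated the drug least. At an assumed 10–20%, that is 3–6 of 30.

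The documents do not support the stronger conclusions that adverse-event follow-up is lost, that these patients necessarily have no day-90 outcome, or that a day-42 value from the exit visit falls outside the protocol. The conclusion rests on nominal infusion days and on reading 5.9's removal as making the patient a 5.7 dropout. It is worth acting on because the correction is cheap and the sample is small.

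**What to change.** Reconcile 5.4, 5.7 and 5.9 by separating two events: stopping carfilzomib and leaving the study.

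1. In 5.9, state that patients who stop drug, including for toxicity, stay in the study for data collection under 5.4 unless they withdraw consent. Day 28, 42 and 90 values come from record review, and the adverse-event questions are asked by telephone under 6.2.2 when the patient does not attend.
2. In 5.7, keep the visit within 30 days of the last infusion, described as an addition to the scheduled data and not a replacement for them.
3. In 5.13, set one rule for all patients for assigning samples to day 42: the in-window sample nearest day 42, with the actual day recorded. An exit-visit sample is used if it is the nearest.

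Nothing here changes when or why drug is stopped.

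The cost is wording in three sections plus slightly more record review and telephone contact, both already in the protocol. The change cannot create DSA or FEV1 values that routine care does not generate, so the number of patients with each value should be reported at each time point, for those who stopped early and those who completed.
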